**SUB-ANALYSIS** will attempt to determine the factors associated with successful RCT outcomes. To accomplish this, we will use our primary outcome as the dependent variable. Fetal factors (age at diagnosis), SVA characteristics (heart rate; arrhythmia pattern; SVT subtypes) and treatment metrics (agent(s); dose) will be considered as potential independent variables. In a first, all variables will be evaluated separately in univariable

logistic regression models. Those with p-values <0.20 in those models will then be selected for further evaluation in a bootstrap bagging algorithm (500 random resamples). Those variables with high reliability (selected in >50% of the random resamples) will be included in a multivariable logistic regression model (PROC LOGISTIC) with likelihood ratio test to determine regression model fit, Wald chi-square test from maximum likelihood estimates (Fisher's scoring technique) to determine statistical significance of the therapy arm and c-statistic from the regression model's area under the curve (AUC) to measure model accuracy with backward selection of variable (p<0.05 to enter) to obtain a final model. Effect size estimate and standard error will be converted into odds ratio with 95% CI to facilitate comparisons of effect size between the different covariates. This final model would indicate factors associated with greater odds of positive outcome and, providing that analog results are found between the effects of 1st line therapy between the 2 models (primary RCT analysis as above and sub-analysis).

**FREQUENCY OF ANALYSIS.** Pre-specified interim analyses of the 3 strata will be performed separately at 50% of enrolment. Each analysis will focus on the primary outcome and safety report including review of between-groups differences and individual review of AEs, other maternal, fetal and infant outcomes, and other safety concerns, if any. All interim analyses will be blinded (with potential un-blinding at the request of the DSMB) as to not influence the final analysis.

**SUBGROUP ANALYSIS.** Additional subgroup analyses will include comparisons with registry participants and impact of tachycardia rates: 1) cardioversion rates over time of RCT participants with SVT and AF  $\pm$  hydrops; and 2) tachycardia rates of cases with persistent SVA at  $\pm$ 1 week of acute therapy (all arms).

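### The sub-analysis reports only the predictors that survive selection, with ordinary odds ratios and an uncorrected c-statistic, so weak factors and model accuracy will look better than they are

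*Combined protocol and SAP*

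**What the plan says.** Section 7.11 (Sub-analysis) takes the primary outcome as the dependent variable and "will attempt to determine the factors associated with successful RCT outcomes". The named candidates are "Fetal factors (age at diagnosis), SVA characteristics (heart rate; arrhythmia pattern; SVT subtypes") together with "treatment metrics (agent(s); dose) will be considered as potential independent variables". That makes six in all.

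Three filters follow, all on the trial data:

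1. Each candidate is tested alone. "Those with p-values <0.20 in those models will then be selected for further evaluation in a bootstrap bagging algorithm (500 random resamples").
2. Candidates are kept if "selected in >50% of the random resamples". The rule that decides selection within a resample is not given.
3. A multivariable logistic model is fitted "with backward selection of variable (p<0.05 to enter) to obtain a final model".

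For the resulting model, "Effect size estimate and standard error will be converted into odds ratio with 95% CI to facilitate comparisons of effect size" between covariates, and the c-statistic is the "area under the curve (AUC) to measure model accuracy". Reporting is described for this final model only. The documents provide no shrinkage, optimism correction, validation set or selection-adjusted interval, and they do not label the sub-analysis exploratory. Earlier in Section 7.11 the three RCTs are to be analysed separately as a general rule. The sub-analysis does not say whether it follows that rule or pools.

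**The concern.** An estimate that is reported only because it passed a significance test is, on average, further from 1 than the truth. The effect is strongest for weak factors, which pass mainly when chance has pushed them outward. The bootstrap step does not correct this: it only chooses variables, it starts after the p<0.20 screen, and the odds ratios and standard errors still come from one fit to the data used for selection. A c-statistic computed on those data is optimistic for the same reason.

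At stake is the list of prognostic factors the trial would publish. Weak or irrelevant factors could appear stronger and more certain than they are, and the model could appear to separate outcomes better than it would in new patients. Comparing effect sizes between covariates is a stated aim, and it suffers because the bias differs between weak and strong factors.

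**Working it through.** **Inputs from the documents.** Section 3.2 gives success rates of 30% vs 50% (RCTs A and C) and 55% vs 75% (RCT B), two-sided 0.05, 80% power, and 186, 178 and 186 participants. Section 7.11 gives the six candidates, the three thresholds and 500 resamples.

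**Assumptions not in the documents.** Six one-parameter, mutually independent candidates; backward selection at p<0.05 inside each resample; the covariate odds ratios shown below.

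**Step 1: reproduce the planned size.** With pooled variance and no continuity correction, n per arm = [1.96√(2p̄(1−p̄)) + 0.8416√(p₁(1−p₁)+p₂(1−p₂))]² / (p₂−p₁)².
- A and C: (1.3579 + 0.5708)² / 0.04 = 93.0, so 93.
- B: (1.3221 + 0.5551)² / 0.04 = 88.1, so 89.
- Total: 186 + 178 + 186 = 550, as stated.

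**Step 2: information available.** The rarer outcome numbers 186 × 0.40 = 74.4 (A, C) and 178 × 0.35 = 62.3 (B). Per candidate, with six, that is 12.4 and 10.4. For a four-term model it is 18.6 and 15.6.

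**Step 3: simulate the written procedure at N=186.**

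Effect set 1 assumes odds ratios 2.34 (arm), 1.35, 1.22, 1.65, 1 and 1, with 500 simulated trials and, for speed, 60 resamples each. The last column shows terms with p<0.05 in a full model without selection, so both columns are conditioned on significance.

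| True OR | Mean OR when retained | Mean OR, full-model terms with p<0.05 |
|---|---|---|
| 1.22 | 1.55 (coverage 89%) | 1.54 (coverage 87%) |
| 1.65 | 2.37 | 2.37 |
| 2.34 (arm) | 2.77 | 2.81 |

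Repeat runs gave 1.53 to 1.55 for the first row and 2.33 to 2.37 for the second. The c-statistic was 0.66 as reported and 0.61 in new data.

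Effect set 2 assumes an arm odds ratio of (0.5/0.5)/(0.3/0.7) = 2.33, a binary factor at 1.50, a continuous factor at 1.35 per SD, and three noise factors, with 1,000 trials and the full 500 resamples.

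| True OR | Mean OR when retained | Coverage when retained | Full model, all terms: mean OR (coverage) |
|---|---|---|---|
| 1.50 (binary) | 2.25 | 90.0% | 1.49 (94.8%) |
| 1.35 per SD | 1.57 | 94.5% | 1.39 (95.1%) |
| 2.33 (arm) | 2.69 | 96.4% | 2.42 (94.3%) |

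The c-statistic was 0.657 as reported and 0.613 in 20,000 new subjects. At least one of the three noise factors entered 14.8% of final models. Three independent 5% tests would give 1 − 0.95³ = 14.3%, so bagging gives no visible protection beyond the final test.

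**Step 4: no true effects.** With 500 resamples, 25.7% of analyses still ended with at least one factor (20% to 24% in runs with other settings). Six independent 5% tests would give 1 − 0.95⁶ = 26.5%. When a factor was retained, the c-statistic averaged 0.598 against 0.500 in new subjects. The interval of a retained null factor cannot cover 1, because retention at p<0.05 excludes it.

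**Step 5: pooled, N=550, effect set 2.** Retained odds ratios averaged 1.69 (true 1.50), 1.38 (true 1.35) and 2.34 (true 2.33). Coverage was 94% to 97%. The c-statistic was 0.655 against 0.642. A noise factor still entered 14.3% of models.

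**The case against.** A reader might infer that the screening and bagging themselves create the bias, so that dropping them removes it. Step 3 does not support that. Full-model terms singled out for p<0.05 are inflated just as much, and with no true effects the full model flags at least one term about as often (28%, against 23% for the planned procedure in the same run). The gain comes from showing every term, and it is lost if readers pick out the significant ones.

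A reader might also infer that all the intervals are too narrow. They are not: the arm and the 1.35-per-SD factor kept roughly 95% coverage or better. Under-coverage is confined to weak and null factors.

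Other points also stand. The sub-analysis is worded as an attempt, no prediction tool is planned, and the c-statistic is the same routine output specified for the primary model. The reading of the final model is tied to agreement with the primary analysis on first-line therapy. That is a safeguard, but the sentence is unfinished and covers only the arm, not the other covariates. Six candidates cannot all apply in RCT A, because SVT subtypes have no meaning in atrial flutter. Nor do the documents show that selection is needless with all six candidates: 10 to 12 rarer outcomes per candidate is workable rather than ample.

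**Conclusion.** The concern holds in a limited form. If the sub-analysis is run within each RCT, its c-statistic will probably be too high (about 0.66 against 0.61, or 0.60 against 0.50 if nothing matters), and the weak factors it retains will be exaggerated, with coverage near 89% to 90%. Strong factors are affected much less, and pooling shrinks the bias. The direction follows from the written procedure. The sizes depend on the assumed effects, the independence of candidates and the assumed within-resample rule.

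This is a low-priority improvement. The documents give no ground for extending it to the trial's main result: the primary arm comparison in Section 7.11, the sample size in Section 3.2 and the stopping rule in Section 5.4 do not use the selected model.

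**What to change.** - Label the sub-analysis exploratory and state whether it is run per RCT or pooled.
- In each RCT, fit one pre-specified logistic model with randomised arm, age at diagnosis, heart rate and arrhythmia pattern. Report every term whatever its p-value, without singling out the significant ones. This leaves about 16 to 19 rarer outcomes per term.
- Add SVT subtype in RCTs B and C only if it is adequately recorded, since Section 2.2 does not require subtypes to be told apart. With three mechanisms it adds two terms, giving six terms and 62.3/6 = 10.4 (B) or 74.4/6 = 12.4 (C) rarer outcomes per term.
- Leave dose out of this baseline model, because Section 7.7 lets the physician change it after treatment starts. Report it separately as descriptive.
- Give a bootstrap optimism-corrected c-statistic.
- If selection is kept, repeat every step, including the p<0.20 screen, inside each resample. State the selection rule used there, report all candidates, and replace the entry criterion attached to backward selection with a criterion for staying in.

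The cost is a change of SAP wording and, for the pre-specified model, less programming than now planned. The downside is that reported effects and accuracy will look less striking.

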**3.2 SAMPLE SIZE CALCULATIONS.** Based on our survey results and the retrospective study by [name] et al, we expect 70% of SVA cases to be SVT (50% no hydrops; 20% hydrops) and 30% AF (25% no hydrops; 5% hydrops). Survey II suggests that an average of 2.3 SVT/no hydrops, 1.21 AF/no hydrops and 1.03 treated SVT/hydrops cases/year/center will be eligible for RCT enrolment, with average consent rates of 81%. Sample size calculation for 2-arm treatment comparisons was performed using PASS (Power and Sample Size) v12 (NCSS, LLC, Kaysville, Utah, USA). To calculate sample size requirements for this study we expected the proportion of patients with normal primary outcome to be 55% with SVT without hydrops, 30% with AF without hydrops, and 30% of SVT with hydrops with the inferior treatment arm (i.e. the null hypothesis). We aim to detect an improvement of +20% in the proportion of patients with a normal primary outcome with the superior RCT arm (i.e. 75% for SVT without hydrops; 50% for AF without hydrops and SVT with hydrops; i.e. the alternative hypothesis). The test statistic used is the two-sided Likelihood Ratio test which is equivalent to the Wald chi-square for logistic regression models which will be used to analyze our primary outcome. The significance level of the test of significance was targeted at 0.05, with a power of 80%. Assuming those metrics, we will need 550 RCT participants, with a minimum number of patients in each of the three RCTs of:

**AF without hydrops (RCT A):** 186 (93/arm) treated cases ← 232 approached cases with 80% consent rate

**SVT without hydrops (RCT B):** 178 (89/arm) treated cases ← 222 approached cases with 80% consent rate

**SVT with hydrops (RCT C):** 186 (93/arm) treated cases ← 232 approached cases with 80% consent rate

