The **PRIMARY OUTCOME** (proportion of term deliveries without SVA) will be a binary outcome (yes/no). For this type of outcome, the proportion of participants in each therapy arm will be compared using logistic regression models (PROC LOGISTIC) with likelihood ratio test to determine regression model fit, Wald chi-square test from maximum likelihood estimates (Fisher’s scoring technique) to determine statistical significance of the therapy arm and c-statistic from the regression model’s area under the curve (AUC) to measure model accuracy. Effect size estimate and standard error will be converted into odds ratio with 95% confidence (95% CI) limits to facilitate comparisons between the different trials.

**SECONDARY OUTCOME** will also be expressed as binary variables (incl. proportions of participants: requiring 2nd line therapy and 3rd line therapy; with SVA recurrence on maintenance therapy; delivery without SVA termination; death <1 month; etc.) will be assessed between the different therapy arms in the same way as the primary outcome. For outcomes with time dependent variables (proportion of participants with cardioversion over time; timing of mortality from initiation of therapy), Kaplan-Meier survival curves will be used to depict the event proportion over time for each group. Single phase parametric hazard regression model (PROC PHREG) will be used to compare the 2 therapy arms (with likelihood ratio test to determine regression model fit and maximum likelihood estimates chi-square to determine statistical significance of the therapy arm. Effect size estimate and standard error will be converted into hazard ratio with 95% CI to facilitate comparisons between the different trials. Finally, for outcomes with continuous variables (average gestational age at birth/birth weight z-score; average days of neonatal hospitalization related to SVA therapy), linear regression models using maximum likelihood estimates for parameter estimation will be used (PROC GENMOD: Akaike's information criterion (AIC) criterion to assess regression model fit; Wald chi-square test from maximum likelihood estimates). Effect size estimate and standard error will determine the difference between the therapy arms in the same original units of measurement as the outcome.

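### The sub-analysis compares the first-line therapy effect with the primary analysis, yet its selection steps can drop the randomised arm, which usually leaves nothing to compare when the primary result is null or weak

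*Combined protocol and SAP*

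**What the plan says.** The primary analysis (7.11, Primary outcome) compares the arms by logistic regression and names no covariate, so I read it as unadjusted. The result is reported as an odds ratio: "Effect size estimate and standard error will be converted into odds ratio".

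The Sub-analysis paragraph of 7.11 looks for factors associated with a good primary outcome. Besides fetal and arrhythmia characteristics, "treatment metrics (agent(s); dose) will be considered as potential independent variables". Every candidate is first tested alone: "Those with p-values <0.20 in those models will then be selected for further evaluation", namely bootstrap bagging with 500 resamples. Variables chosen in more than 50% of resamples enter a multivariable logistic model, which is reduced by backward selection at p<0.05. Nothing exempts the randomised arm from any of these steps. Yet the paragraph also says that the multivariable model will test the significance of the therapy arm.

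Its last sentence says that the final model indicates factors linked to better odds of success. It then adds a proviso about first-line therapy in the two models, "providing that analog results are found between the effects of", and ends without a main clause. What counts as analogous is not defined.

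**The concern.** The comparison needs a therapy effect in both models. The selection rule guarantees one only in the primary model. A p-value decides whether the second effect exists, and that p-value comes from the same patients and much the same contrast as the primary test. Two things follow. When the primary result is null or weak, the final model will usually hold no arm term. When the term is there, it has passed a significance filter, so its size is biased away from no effect and its agreement with a significant primary result is close to built in. A comparison that is available mainly when it must succeed says little about whether the prognostic model is sound.

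The scale is a lesser issue. An odds ratio adjusted for prognostic factors is further from 1 than the unadjusted one even when randomisation is perfect and both models are right.

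**Working it through.** **Inputs from section 3.2.** Success is assumed to be "55% with SVT without hydrops, 30% with AF without hydrops, and 30% of SVT with hydrops with the inferior treatment arm", and "We aim to detect an improvement of +20% in the proportion of patients with a normal primary outcome", with two-sided alpha 0.05, power 80%, 93 per arm in RCT A and C, and 89 per arm in RCT B.

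**The plan's own figure.** n per arm = [1.96√(2p̄(1−p̄)) + 0.842√(p₁(1−p₁)+p₂(1−p₂))]² / (p₂−p₁)². For 30% v 50% this gives 93.0, so 93; for 55% v 75% it gives 88.1, so 89. Both match.

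**Step 1: the arm judged by its unadjusted p-value.** All possible pairs of success counts were enumerated with their binomial probabilities. The test is z = log OR / √(1/a + 1/(n−a) + 1/b + 1/(n−b)), where a and b are the successes per arm.

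| True rates | n per arm | P(p<0.20) | P(p<0.05) |
|---|---|---|---|
| 40% v 40% | 93 | 20% | 4.7% |
| 30% v 40% | 93 | 56% | 30% |
| 30% v 50% | 93 | 94% | 79% |
| 55% v 75% | 89 | 94% | 81% |

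**Step 2: the whole selection path, by simulation.** Assumptions not in the documents: three other covariates, one of them prognostic with an odds ratio of 1.8 per SD; backward selection at p<0.05 inside each resample; 100 resamples instead of 500. Two runs were made, of 300 and 400 trials per scenario (30% v 40% in the first only).

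| True rates | Arm absent from final model |
|---|---|
| 40% v 40% | 97%, 95% |
| 30% v 40% | 72% |
| 30% v 50% | 18%, 18.5% |
| 55% v 75% | 21%, 19% |

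With a stronger covariate (odds ratio 3 per SD, 250 trials) the 30% v 50% figure was 18.4%.

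Absence follows the primary result. In the 400-trial runs at the design effects, the arm was dropped in 6 of 318 (RCT A/C) and 10 of 322 (RCT B) trials with a significant primary result, against 68 of 82 and 66 of 78 without one.

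**Step 3: inflation when the arm is kept.** At 30% v 40% the true odds ratio is (0.4/0.6)/(0.3/0.7) = 1.56. Suppose 28 of 93 succeed in one arm. The other arm then needs at least 41 of 93 to reach p<0.05: log OR = 0.605, SE = √(1/28+1/65+1/41+1/52) = 0.308, z = 1.96. That is already an odds ratio of 1.83. Averaging log OR over all significant outcomes in the Step 1 enumeration and exponentiating gives about 2.25 against the true 1.56. At 30% v 50% the same average is 2.63 against 2.33.

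**Step 4: adjusted against unadjusted odds ratio.** Take a balanced normal covariate score x with SD s on the logit scale (assumed). Solve E[1/(1+exp(−(a_k + s·x)))] = p_k for each arm, with x standard normal; the adjusted odds ratio is exp(a₂−a₁).

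| True rates | Unadjusted OR | s = 0.5 | s = 1.0 |
|---|---|---|---|
| 30% v 50% | 2.33 | 2.45 | 2.77 |
| 55% v 75% | 2.45 | 2.58 | 2.92 |

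The risk difference is 20 points throughout. For sampling error, SE(log OR) = √{[1/(p₁(1−p₁)) + 1/(p₂(1−p₂))]/n} = 0.307 for RCT A/C and 0.325 for RCT B. The unadjusted 95% intervals at the design effect are therefore 1.28 to 4.26 and 1.30 to 4.64, which contain every adjusted value in the table.

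**The case against.** A reader might infer that the sub-analysis is accepted only if the two effects agree, and that the check cannot work. The documents do not support that. The statement about prognostic factors comes before the proviso, and the proviso has no consequent, so no acceptance rule is written. Nor is the check the only safeguard on the factors found: bagging, a likelihood-ratio fit test and the c-statistic apply too.

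It is equally tempting to say that the check rejects good models because the two odds ratios differ. But the plan does not say that the ratios must be equal, and the gap is small beside the noise. In the simulated trials that kept the arm, direction agreed every time. The adjusted value lay inside the unadjusted interval in 326 of 326 and 324 of 324 trials with the moderate covariate, and in 195 of 204 with the strong one. A loose rule would work whenever the arm is there.

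Two further arguments have weight. Testing the therapy arm in the multivariable model presupposes that it is present, so the authors may intend to keep it. And a null primary result with the arm unselected is a kind of concordance. What stands is that the written rule lists the agent among the selectable candidates and never says it is retained. An unselected arm gives no estimate or interval to compare.

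**Conclusion.** The point holds as a minor one. The selection rule can remove the term that the comparison needs: in roughly 95% of trials with no drug difference, 70% at a 10-point difference from 30%, and 20% at the design effect. When the term survives, its size is inflated by selection. The difference between adjusted and unadjusted odds ratios is real but secondary, and argues only against requiring equality.

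The unadjusted passing rates in Step 1 follow from the plan's sample sizes and the stated true rates. The absence rates and the odds-ratio gap also rest on assumed covariate strengths, and the absence rates on an assumed selection rule within resamples, since the documents give neither. Equating the listed agent with the randomised arm is my reading. The sub-analysis is exploratory, so the primary test, alpha and sample size are untouched.

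**What to change.** In the Sub-analysis paragraph of 7.11:

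- State that the randomised arm, as allocated, is exempt from the p<0.20 screen and is kept in every resample model and in the final model whatever its p-value. Apply selection only to the other factors. The probability that the arm is absent then falls to zero, and its estimate is no longer filtered by its own significance.
- Finish the sentence: say what follows if the two analyses agree and if they do not.
- Define agreement as the same direction with compatible confidence intervals. Preferably, compare the primary risk difference with the standardised risk difference from the final model, that is, mean predicted success with all participants set to one arm minus the mean with all set to the other. This removes the odds-ratio scale problem but is an option, not a necessity. Equality of odds ratios should not be the criterion.

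The cost is a few sentences and a few lines of code, with no new data.
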